### iii. Sample Size

We plan to enroll up to 100 adult surrogates of CA patients in this study. All participants will be English and/or Spanish speakers. Participants will be enrolled and randomized (using a 2:1 allocation) to either the active informational intervention or the care as usual control group. Enrollment will end once 30 participants in the intervention arm have completed their participation in the study.

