#### **viii. Randomization**

[name] will be responsible for generating the randomization allocation table for the REDCap randomization module, which will assign participants to arms.

Method:

1. Before study launch, [name] will build a master randomization allocation table using Excel. This allocation table will yield arm assignments for 100 study participants (67 in the intervention arm, 33 in the control arm).
2. [name] will upload the allocation table to the REDCap randomization module.
3. Once the study launches, REDCap will switch to production mode, and the randomization module will be locked. Randomization assignments cannot be changed going forward.

4. When a new participant is recruited, study coordinators will click “Randomize” for a new record in REDCap. This will yield the arm assignment for the new participant, as determined by the pre-made allocation table.

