**iii. Statistical Methods**

**Statistical approach for Aim 1:** *Enroll up to 100 (until 30 in the intervention arm) surrogates of CA patients to (Aim 1a) pilot recruitment and randomization procedures, (Aim 1b) estimate retention rate at 3 months, and (Aim 1c) assess the engagement and utilization metrics through the app for frequency of access and time spent on packages.*

**Aim 1a.** Based on our prior studies with surrogates of CA patients who survive to hospital discharge, 8 surrogates/month will be eligible to participate in the proposed study and <5 participants/month will be considered not meeting the outcome. **Aim 1b.** Based on our prior successes, we expect retention rates of ~90%. Since this is an

interventional study, the proportion of participants who complete the 3-month assessments <80% will be considered as not meeting the outcome. A sample size of  $N = 30$  surrogates results in a 95% confidence interval of this estimate equal to 79% – 100%, providing sufficient precision for study planning. **Aim 1c.** Acceptability will be assessed by recording reasons for dropout, reasons for noncompliance, and querying participants about burden at 3 months. We will consider scale completion >90% acceptable. The application can track the utilization of the content, time spent on each module of the packages, and participants' review and content feedback.

**Statistical approach for Exploratory Aims 1a-c.** *Estimate the association of intervention v. control with the surrogate's uncertainty levels at 3 months post-discharge (Exploratory Aim 1a), cardiac anxiety, and PTSS at 3 months post-discharge (Exploratory Aim 1b), and explore the lagged associations of uncertainty with cardiac anxiety and PTSS (Exploratory Aim 1c).* We will compute 95% bootstrap confidence intervals around the mean difference in **(1a)** uncertainty in illness total scores; **(1b)** total scores on the cardiac anxiety questionnaire and PCL-5 between intervention and control conditions and **(1c)** the associations between surrogates' uncertainty scores and cardiac anxiety as well as PTSS accounting for enrollment, discharge, and 3 month scores. The lower bounds of these correlations will be used for sample size calculations when planning the larger study to account for uncertainty in small samples.  $N = 30$  has been recommended as sufficient for pilot studies.

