**Statistical approach for Exploratory Aim 2:** *Obtain a preliminary estimate of the association of intervention v. control with surrogates' sleep duration within the first one week after hospital discharge.* We will compute 95% bootstrap confidence intervals around the mean difference in duration of sleep over the one week post-discharge, between intervention and control participants.

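### The bootstrap type for the arm-difference intervals is not named; with about 15 controls, percentile, basic and BCa intervals cover about 92% to 94% instead of 95%, and a Welch t interval would correct this

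*Combined protocol and SAP*

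**What the plan says.** Section 3.b.iii (Statistical Methods) gives one method for the arm comparisons. For Exploratory Aims 1a and 1b: "We will compute 95% bootstrap confidence intervals around the mean difference in" uncertainty, cardiac anxiety and PCL-5 total scores. For Exploratory Aim 2, the interval is for the "mean difference in duration of sleep over the one week post-discharge, between intervention and control participants". Neither paragraph states the bootstrap type, the number of resamples, whether resampling is within arm, or any small-sample correction. No standard deviation or distribution is given for any outcome.

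On arm sizes, section 3.a.iii (Sample Size) says "Participants will be enrolled and randomized (using a 2:1 allocation) to either the active informational intervention or the care as usual control group", and then "Enrollment will end once 30 participants in the intervention arm have completed their participation in the study". Section 3.a.viii (Randomization) sets the ceiling: "This allocation table will yield arm assignments for 100 study participants (67 in the intervention arm, 33 in the control arm"). The number of controls expected to be analysed is not stated.

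**The concern.** The percentile, basic and BCa bootstraps share a small-sample weakness. Resampling an arm of n people reproduces a variance with divisor n instead of n − 1, and none of the three widens the interval as a t quantile does to allow for an estimated variance. Both effects shorten the interval, and both matter when the smaller arm has about 15 people. They occur with normal data too, so the problem does not depend on skew, although skew can add to it.

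These intervals are the only planned output for the arm comparisons in Exploratory Aims 1a, 1b and 2. If they run short, a reader is told that the pilot pins down the differences better than it does. Leaving the type open also means that it can be chosen after the data are seen, in an unblinded trial.

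**Working it through.** **The plan's own figure.** The only precision figure in section 3.b.iii is for retention, with N = 30 and 90% expected. The Wald interval is 0.90 ± 1.96 × √(0.9 × 0.1 / 30) = 0.90 ± 0.107, or 79.3% to 100.7%. Cut at 100%, this reproduces the stated 79% to 100%. No width or coverage is given for the bootstrap intervals, so there is no plan figure to check them against.

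**Arm sizes.** 30 intervention completers at 2:1 with equal retention in the arms gives 30 / 2 = 15 controls. The table's ceiling is 67 v 33. An intermediate case is 44 v 22.

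**Approximation by hand, normal scores with SD 1 in each arm, 30 v 15.**
- Unbiased variance of the difference: 1/30 + 1/15 = 0.1000.
- Bootstrap (divisor n) variance: 29/30² + 14/15² = 0.0322 + 0.0622 = 0.0944.
- Effective multiplier of the usual standard error: 1.96 × √(0.0944/0.1000) = 1.905.
- Welch degrees of freedom: 0.1² / [(1/30)²/29 + (1/15)²/14] = 28.1, with t quantile 2.048.
- Width ratio: 1.905 / 2.048 = 0.93. Coverage: P(|t₂₈.₁| < 1.905) = 93.3%.

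The same steps give multiplier 1.923, 42.1 degrees of freedom and coverage 93.9% at 44 v 22, and 1.935, 63.8 and 94.3% at 67 v 33.

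**Simulation.** 4,000 trials per cell, 1,999 resamples within arm, true difference zero, the same distribution in both arms; Monte Carlo error about 0.3 to 0.5 points. The outcome shapes are assumptions. Coverage (%) at 30 v 15:

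| Interval | Normal | Skew 1.0 | Skew 1.4 | Exponential (skew 2) | Lognormal (σ 0.8) |
|---|---|---|---|---|---|
| Percentile | 93.6 | 92.9 | 92.5 | 92.2 | 91.8 |
| Basic | 93.6 | 93.3 | 92.9 | 93.6 | 94.2 |
| BCa | 93.5 | 92.7 | 92.0 | 90.6 | 88.5 |
| Studentised | 95.1 | 94.2 | 93.5 | 92.8 | 91.9 |
| Welch t | 95.2 | 95.1 | 94.4 | 95.1 | 94.8 |

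A second run (8,000 trials per cell, 1,000 resamples, normal to skew 1.6) gave percentile 92.3% to 93.1%, basic 92.6% to 93.5% and Welch 94.6% to 95.1% at 30 v 15.

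**Width.** With normal scores at 30 v 15 the mean widths are 1.189 SD (percentile) and 1.284 SD (Welch). The ratio is 1.189 / 1.284 = 0.926, so the percentile interval is between 7% and 8% short. The second run gave a ratio of 0.92.

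**More controls.** For normal to skew 1.4, percentile coverage is 93.4% to 93.9% at 44 v 22 and 93.5% to 94.2% at 67 v 33. With normal scores the Welch interval is 1.047 / 0.995 = 1.05 and 0.848 / 0.819 = 1.04 times the percentile width.

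**Unequal spread.** At 30 v 15 with lognormal scores and an intervention-to-control scale ratio of 0.8, coverage is 90.7% (percentile), 92.6% (basic), 88.3% (BCa), 91.0% (studentised) and 94.0% (Welch).

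**The case against.** The strongest reply is that the plan is underspecified, not wrong. It says only that the intervals are bootstrapped, which already permits the studentised type. A reader might infer that every common bootstrap falls short here. That is not so: the studentised version covers 94% to 95% for normal to mildly skewed scores, and falls below 93% only under strong skew. This part of the reply stands, and limits the point to the percentile, basic and BCa types.

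The second reply is that 15 controls is near the low end. Completion comes three months after discharge, and enrollment continues until the thirtieth intervention participant reaches it. If 5 to 8 people a month enrol during that lag (section 3.b.iii gives 5 as the feasibility threshold and 8 as the number eligible), 15 to 24 more are randomized. About a third, 5 to 8, are controls, making 20 to 23 if all are followed up. This also stands; the shortfall is then smaller but does not vanish.

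Other stronger readings are not supported:
- *That these bounds will size the larger study.* The planning sentence in section 3.b.iii refers to lower bounds of correlations, which fits the uncertainty–distress associations of Exploratory Aim 1c. It does not clearly cover the mean differences.
- *That sleep will have fewer controls.* All participants receive the device at discharge, before three-month attrition, and no rate of device loss is given.
- *That a 5% test becomes a 6% to 8% test.* No test or decision rule is attached to these intervals.
- *That an interval from a baseline-adjusted regression is available as a substitute.* The plan contains no such model, and neither cardiac anxiety nor sleep is measured at baseline.

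**Conclusion.** The concern holds in a limited form. The bootstrap type is unstated. At 30 v 15, percentile, basic and BCa intervals fall about 1 to 3 points short of 95% for near-normal to moderately skewed scores, with BCa as low as 88.5% under the strongest skew tried. The percentile interval is about 8% too narrow. With 22 to 33 controls the percentile shortfall is about 1 to 1.5 points.

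These figures rest on three assumptions: about 15 controls, inferred from the 2:1 ratio and equal retention; outcome shapes, which the documents do not give; and the same shape in both arms, with one unequal-spread variant. The hand calculation shows that the shortfall is present with normal data. Its exact size under skew depends on the shape assumed. Because the aims are exploratory and the intervals wide in any case (1.19 v 1.28 SD), interpretation would rarely change. It is a minor improvement worth making because it is nearly free.

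**What to change.** In section 3.b.iii, state that the main interval for the mean difference between arms in Exploratory Aims 1a, 1b and 2 is the Welch t 95% interval. If a bootstrap is kept as a supporting analysis, name the studentised (bootstrap-t) version, resampled within arm, with the number of resamples fixed in advance.

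Welch is the better main choice because its coverage was 94.4% to 95.2% for every shape at 30 v 15 with equal spread, and 94.0% in the unequal-spread lognormal case, where the studentised bootstrap fell to 91.0%.

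The cost is one sentence of text and intervals about 4% wider than percentile intervals at 67 v 33, rising to about 8% or 9% at 30 v 15. No new data or change in sample size is needed.

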## 1. Administrative Information

a. **Title:** Removing Surrogates Uncertainty to Reduce Fear and Anxiety after Cardiac Events (RESURFACE): A Randomized Pilot Intervention Study

a. **Public Title:** RESURFACE

b. **Registration Data:**

a. **Identifying Number:** IRB Number AAAR8497

b. **Primary Sponsor:** NIH/NIA

c. **Contact for Inquiries:**

[name], Principal Investigator

Associate Professor of Neurology (Neurocritical Care)

Dept of Neurology

[name]

[name]

[name]

[contact]

Email: [[contact]](mailto:[contact])

d. **Sites of Recruitment:** Columbia University Medical Center

e. **Health Condition(s) or Problem(s) Studied:** Psychological distress and poor sleep in surrogates of cardiac arrest (CA)

f. **Key Inclusion and Exclusion Criteria:**

*Inclusion Criteria:*

- 18 years of age or older
- Surrogate of an adult CA patient
- English- or Spanish-speaking
- Has a working smartphone, tablet, laptop, or other device with internet access

*Exclusion Criteria:*

- Any medical and/or psychiatric impairment precluding them from complying with the protocol
- Non-English and non-Spanish speaking
- Lack of internet/device access

- Surrogate of an adult CA patient who passed away
- Cannot be reached for initial contact (3 unsuccessful attempts made in ICU)
- Moved to the floor before initial contact can be established

g. **Study Type:** Unblinded two-arm pilot RCT of study intervention consisting of three online packages delivered in the ICU, inpatient floor, and at home for the intervention arm and care as usual for the control arm.

h. **Date of First Enrollment:** Pending

i. **Target Sample Size:** Up to 100 participants (recruiting 2:1 until at least 30 intervention arm participants conclude participation)

j. **Recruitment Status:** Not yet recruiting

c. **Roles and Responsibilities:**

**[name], MPH** [[contact]](mailto:[contact])

Principal Investigator, Associate Professor of Neurology (Neurocritical Care) and Director of the NeuroCardiac Comprehensive Care Clinical & Research Program.

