## b. Objectives

We will test the feasibility and acceptability of Heartsight, an online informational intervention program developed by a multidisciplinary team of researchers and patient-surrogate stakeholders. It is a repository of bite-sized, simplified, information packages to be delivered at specific time points in the illness course: an **Understanding Cardiac Arrest** package in the ICU, a **Preparing for Discharge** package on the floor, and a **Focusing on You** package providing information on self-care and self-efficacy at 1 month post-discharge. Serial measurements of illness uncertainty and psychological distress (PTSS keyed to the cardiac event) will be performed at enrollment, discharge, and 3 months after discharge. We will objectively assess sleep duration via actigraphy for 1 week after hospital discharge.

**Aim 1:** Enroll up to 100 surrogates of CA patients to (**Aim 1a**) pilot recruitment and randomization (2:1) procedures, (**Aim 1b**) estimate retention rate at 3 months, and (**Aim 1c**) assess the engagement and utilization metrics through the website for frequency of access and time spent on each module of the packages.

**Exploratory Aim 1a:** Preliminary estimate of the association of intervention with the surrogate's uncertainty levels at 3 months post-discharge.

**Exploratory Aim 1b:** Preliminary estimate of the association of intervention with the surrogate's cardiac anxiety and posttraumatic stress at 3 months post-discharge.

**Exploratory Aim 1c:** Explore the lagged associations of uncertainty with cardiac anxiety and PTSS.

**Exploratory Aim 2:** Estimate the association of intervention with surrogates' sleep duration within the first week after hospital discharge.

[figure not shown]

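### Exploratory Aim 1c invokes enrollment scores, but cardiac anxiety is first measured at discharge, so two of the three uncertainty-to-later-anxiety lags cannot be adjusted for prior anxiety (minor)

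*Combined protocol and SAP*

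**What the plan says.** All references are to the combined protocol and SAP.

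- **Aim.** Section 2.b states Exploratory Aim 1c as: "Explore the lagged associations of uncertainty with cardiac anxiety and PTSS".
- **Analysis.** Section 3.b.iii (Statistical Methods) plans bootstrap 95% intervals for the associations of uncertainty scores with "cardiac anxiety as well as PTSS accounting for enrollment, discharge, and 3 month scores".
- **Use.** The same paragraph continues: "The lower bounds of these correlations will be used for sample size calculations when planning the larger study".
- **Schedule.** Sections 3.a.ix and 3.b.i place the Mishel uncertainty scale and the PCL-5 in Surveys 1, 2 and 3. The CAQ is in Surveys 2 and 3 only. Survey 2 is given about a day before discharge, after Heartsight Packages 1 and 2 are due to have gone to the intervention arm.
- **Serial measures.** Section 2.b says: "Serial measurements of illness uncertainty and psychological distress (PTSS keyed to the cardiac event) will be performed at enrollment", and at the two later waves. Cardiac anxiety is not named there.
- **Status.** Section 1.b gives recruitment as "Not yet recruiting".

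**The concern.** The statistical section treats the two outcomes in one sentence and invokes three waves of scores. Only one outcome has three waves. For cardiac anxiety there is no enrollment score to account for, and the plan does not say how the anxiety analysis proceeds without it.

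The lags that start from enrollment uncertainty are the ones affected. Surrogates who are more uncertain in the ICU may already be more anxious in the ICU, and anxiety tends to persist. Without an enrollment anxiety score, a correlation between enrollment uncertainty and later anxiety contains that carry-over as well as any lagged association. A lower confidence bound allows for sampling error and leaves this bias in place. The result matters beyond the pilot because the lower bounds are to be planning inputs for the next trial. The enrollment score cannot be recovered once a surrogate is past that point.

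**Working it through.** **1. Waves available** (Sections 3.a.ix and 3.b.i)

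| Score | Enrollment | Discharge | 3 months |
|---|---|---|---|
| Uncertainty (Mishel) | yes | yes | yes |
| PTSS (PCL-5) | yes | yes | yes |
| Cardiac anxiety (CAQ) | no | yes | yes |

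The plan's three waves are reproduced for uncertainty and PTSS. Cardiac anxiety has two.

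**2. Lags from uncertainty to a later outcome, and whether the outcome was also measured at or before the exposure wave**

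| Lag | Prior anxiety | Prior PTSS |
|---|---|---|
| Enrollment to discharge | no | yes |
| Enrollment to 3 months | no | yes |
| Discharge to 3 months | yes | yes |
| Total | 1 of 3 | 3 of 3 |

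If any anxiety score before the outcome counts, the anxiety total is 2 of 3. The added case adjusts the enrollment-to-3-month lag for discharge anxiety, which is measured after the exposure and may be an intermediate.

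**3. Completers.** Section 3.a.iii ends enrollment at 30 intervention completers. At 2:1 that is 30 + 15 = 45 in total, plus any participants still in follow-up. With all 100 enrolled and the expected retention of about 90%, the total would be 90. I treat 90 as an upper case only.

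**4. How large could the mixing be?** The documents give no correlation, so these inputs are assumptions: an enrollment uncertainty-anxiety correlation rho of 0.3 to 0.5, anxiety stability a of 0.4 to 0.6, and no true lagged association. Carry-over alone then gives a population correlation of rho × a:

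- 0.3 × 0.4 = 0.12
- 0.4 × 0.5 = 0.20
- 0.5 × 0.6 = 0.30

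A typical lower 95% bound at n = 45, by the Fisher-z approximation, is tanh(atanh(r) − 1.960/√42), where 1.960/√42 = 0.302:

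- r = 0.12: tanh(0.121 − 0.302) = −0.18
- r = 0.20: tanh(0.203 − 0.302) = −0.10
- r = 0.30: tanh(0.310 − 0.302) = 0.01

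Simulation with the planned kind of interval (1,000 pilots per scenario, 500 percentile-bootstrap resamples, n = 45) gave:

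| | Unadjusted | Adjusted for enrollment anxiety |
|---|---|---|
| Share of pilots with lower bound above zero | about 14% to 57% | about 3% to 4% |
| Median lower bound | about −0.17 to 0.03 | not needed here |

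In the upper case, n = 90, the unadjusted share was about 21% to 82%.

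**5. Cost of adding the subscale.** Survey 1 has 22 + 7 + 27 + 31 + 20 + 4 = 111 questions. Adding 8 gives 119, and 8/111 = 7.2%. Pro rata on the stated 20 minutes, 20 × 8/111 = 1.4 minutes.

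**The case against.** **The clause may not cover anxiety.** Its last word can refer back to uncertainty scores, and Section 2.b names only uncertainty and PTSS as serial from enrollment. This stands. A reader might infer that the cardiac anxiety part of Aim 1c is impossible, and the documents do not support that: all three lags can be estimated. But the narrower reading supplies no prior anxiety score for the two enrollment lags, and the plan does not state the exception.

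**Adjustment for prior outcome is not promised.** The plan speaks of lagged associations and correlations and specifies no cross-lagged model. This is fair as far as it goes. The case for adjustment rests on the stated use of the bounds for planning.

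**Other baseline scores could help.** Baseline PCL-5, Threat Perception and Intolerance of Uncertainty scores could adjust for part of the carry-over. They do not replace an anxiety score, and the plan does not name them for this purpose.

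**The practical harm is limited.** The share of bounds above zero says little about their size. At n = 45 the typical bound is negative or close to zero and would give no usable planning value. A reader might also infer that the bound will be positive whenever rho × a exceeds tanh(1.960/√42) = 0.294. That threshold applies to the sample correlation. With a population product of 0.20, about 30% of the simulated pilots at n = 45 still had a positive bound.

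**Burden.** Extra questions fall on surrogates in the ICU and bear on the plan's own criterion: "We will consider scale completion >90% acceptable". This stands and is why the fix has a wording-only alternative.

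**Conclusion.** The point holds as a minor one. The wave counts follow directly from the survey schedule and need no assumption: anxiety at or before the exposure exists for 1 of 3 lags, against 3 of 3 for PTSS. Either the clause cannot be carried out for cardiac anxiety, or it is narrower than it reads and leaves two lags without that adjustment.

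The size of the resulting bias cannot be derived from the documents. The simulated figures depend on the assumed correlation, stability and number of completers. They show that a spurious planning value is possible but usually small or unusable.

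A reader might infer that the pilot's other results are compromised. They are not. Feasibility Aims 1a to 1c do not use these scores this way, and the arm difference at 3 months in Exploratory Aim 1b does not need a baseline score.

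A separate wording point concerns the same scale. Section 3.b.iii analyses "total scores on the cardiac anxiety questionnaire and PCL-5 between intervention and control conditions", Section 3.a.ix collects an 8-question fear subscale, and the Survey 2 and 3 lists in Section 3.b.i name no subscale.

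**What to change.** **Preferred, before first enrollment.** Add to Survey 1 the 8-question fear subscale already used in Survey 2. Section 3.a.ix already sends Heartsight access only after the baseline survey is complete, so the order is right. All three lags to later anxiety could then be adjusted, as for PTSS.

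The cost is 111 to 119 questions, about 1.4 minutes pro rata, for surrogates in the ICU. It also means a change to the REDCap baseline survey and probably an IRB amendment. No new instrument or visit is needed, and Survey 2 is already handed out in English or Spanish. Survey 1 follows randomization in an unblinded trial, so the new score would be pre-intervention but post-allocation, as the other baseline scores already are. The plan should say so.

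**If the subscale is not added (wording only), in Section 3.b.iii:**

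- limit the enrollment part of the clause to uncertainty and PTSS;
- adjust only the discharge-to-3-month lag for prior anxiety;
- report the two enrollment-to-anxiety lags as unadjusted for prior anxiety;
- do not use the lower bounds of those two lags to size the larger study.

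**In either case**, state which scores the clause covers, and use one description of the CAQ score in Sections 3.a.ix, 3.b.i and 3.b.iii, naming the fear subscale in the analysis if that is all that is collected.
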